9.2.2. Number and grading of needle adjustments

During or after each intervention, the number of needle adjustments will be reported, if necessary.

The number of needle adjustments to reach the target will be presented using qualitative and quantitative descriptive statistics:

- per needle.
- per lesion (sum per lesion).
- per patient (sum per patient).

Grading of adjustment(s) (minor, medium and major, refer to Section 3.5.2 for definitions) will be presented using frequency and percentage:

- per needle (at least one per needle).
- per lesion (at least one per lesion).
- per patient (at least one per patient).

In addition, quantitative descriptive statistics on the estimated corrective distance (mm) will be presented separately for each grading of adjustment (minor and medium):

- per needle (the highest per needle).
- per lesion (the highest per lesion).
- per patient (the highest per patient).

The highest distance was considered as the worst distance.

Finally, method of adjustment (using Epione® or other [CT guided, freehand]) will be presented in a listing.

9.2.3. Immediate post-intervention ablation success (ablation only)

This secondary criterion determines if the ablation is complete, incomplete or unclear. In a complete ablation, the ablation volume completely covers the lesion, with sufficient MAM of 5 mm. Ablation assessment tool of EPIONE will be collected (complete ablation, incomplete ablation, unclear ablation) and summary statistics for qualitative parameters will be provided per lesion and per patient (the best result per patient).

9.2.4. Long-term performance of intervention using the Local Tumor Progression rate (ablation only)

Patients with tumor ablation will be evaluated for Local Tumor Progression (LTP) on follow-up CT imaging by the physician during the routine follow-up visits. This will be presented by lesion only.

Frequency and percentage of patients with any visible LTP on control imaging will be presented at approximately 6 months and 12 months. 95% CIs will be provided. The CT images of the ablation zone obtained at 1 month-FU routine visit will be considered as baseline imaging. The evaluation at later follow-up visits will be performed by comparing follow-up CT-scans to the baseline.

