Patient placed under general anesthesia. Acquisition of the pre-intervention CT-guided image of the lungs. Confirmation of the prescribed CT-guided intervention realization (if the intervention is not maintained, the patient's exit from the study, for screening failure). Planning with the subject device to visualize the path of needle(s) to the target. Planning validation by the investigator and then insertion of the needle(s) to the targeted area with the subject device. Acquisition of the per-intervention image under CT guidance. Validation of the correct positioning of the needle(s). Completion of the CT-guided intervention with a needle routinely used by the investigator. Acquisition of the post-intervention CT-guided image and evaluation of possible adverse events. In case of interventions on multiple lesions, the absence of a non-reduced major pneumothorax must be confirmed to use the device again for the next intervention. In case of interventions performed on different days on or both lungs treated on two different days, the additional intervention day will be added to the D0 sheet.

- Visit 3: post-intervention follow-up visit at 1 month (D0+2 weeks ≤ D ≤ D0+6 weeks)**

Follow-up of AEs related to the intervention and record of possible new AE/SAEs.

Review of the acquired image (CT-scan or equivalent) of the lungs to evaluate for ablation the ablation site local tumor progression and establish a baseline situation of the treated tumor.

- Visit 4: post-intervention follow-up visit at 6 months (D0+4 months ≤ D ≤ D0+8 months)**

Review of the acquired image (CT-scan or equivalent) of the lungs to evaluate ablation site local tumor progression and evaluation of possible AE/SAEs.

- Visit 5: post-intervention follow-up visit at 12 months (D0+10 months ≤ D ≤ D0+14 months)**

Review of the acquired image (CT-scan or equivalent) of the lungs to evaluate ablation site, local tumor progression and evaluation of possible AE/SAEs.

Sample size	25 patients
Randomisation and blinding	Not applicable.
Statistical analysis method	The statistical analysis will be performed by an external CRO (Delta Data Consultants, Eybens, France). All statistical analyses will be produced using SAS® 9.4 software (Cary, NC, USA)..

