- COMPLETE ABLATION: Ground glass opacity (GGO) induced by the ablation completely covers the targeted tumor minimal 5 mm ablation margins.
- INCOMPLETE ABLATION: GGO covers the targeted tumor but with a margin of <5 mm.
- UNCLEAR ABLATION: Margins cannot be assessed, or the delimitation is not identifiable.

- **Long-term local performance of ablation at 6 and 12 months (ablation only)**

Long-term local performance of ablation is based on local tumor progression (LTP) evaluated from CT images at the 6 and 12 months' Follow-up visit. Follow-up visit at 1 month will be taken as baseline.

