7. DEMOGRAPHIC AND BASELINE CHARACTERISTICS

Demographic and lung tumor characteristics will be presented on the ITT population using summary statistics for qualitative or quantitative parameters:

- Demographic data: age (years), gender, height (cm), weight (kg), Body Mass Index (kg/m²).
- Planned intervention: side of targeted lung (left, right or both [together/separately]), type of CT-Guided percutaneous treatment to be planned:
 - Ablation.
 - Biopsy.
 - Abscess drainage.
 - Fiducial marker insertion.
- Lung tumor type:
 - Primary tumor: NSCLC subtype, TNM stage (or other).
 - Metastatic tumor: primary cancer location.
 - Unidentified.
- Lung lesions:
 - Number of lesions intended to be treated per lung per patient.
 - Lesion details: lung side (left or right) and lobe (upper, lower or medium), lesion location (<10mm to mediastinum, <10mm to hilum, <10mm to pleura), tumor size (cm), estimated intra parenchymal distance (cm), intervention type performed (ablation, biopsy, abscess drainage, fiducial marker insertion).
- Planning with the Epione® device:
 - Number of needle trajectories
 - Needle identification information.

In addition, the following duration parameters will be presented only for the final analysis:

- Procedure time (post-intervention - pre-interventional CT-scan).
- Duration of Epione® device use (end of trajectory guidance – start of procedure planning).
- Duration of guidance (end of trajectory guidance - start of trajectory guidance).

Medical history, comorbidities, concomitant treatments (for the last 3 months) and planning with the Epione® device at inclusion will be described in patient data listings.

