9.1. Primary endpoint

9.1.1. Definition of the primary variable

The primary endpoint is the technical success by lesion of each intervention.

Technical success by lesion is defined as:

When the needle(s) tip(s) reach(es) the target(s) with sufficient accuracy to pursue the intervention, and:

- Robotic needle insertion is performed without adjustment.
- Robotic insertion with only minor or medium adjustment(s).
- Robotic insertion is performed with one robotic major adjustment.

Technical failure by lesion is defined as:

When the needle tip does not reach the target with sufficient accuracy to pursue the intervention:

- If insertion of one or several needle(s) from the skin is fully manual.
- Failure of a robotic major adjustment.

The parameter of the primary endpoint consists of the percentage of robotically assisted lesion targeting and needle placements that were accurate enough to allow the percutaneous intervention.

The investigator will describe the technical success of the procedure for each lesion on a 2-point scale:

- "Is/are the needles positioned accurately enough to allow next step of the intervention?" = "Yes"
- "Is/are the needles positioned accurately enough to allow next step of the intervention?" = "No"

The performance endpoint is defined by "Is/are the needles positioned accurately enough to allow next step of the intervention?" = "Yes".

Note: if a lesion cannot be treated because of a major pneumothorax on the previous lesions treated, the lesion is excluded from the study and is not taken into account in feasibility statistics (negative answer to the question "Was the CT-Guided intervention maintained" with "pneumothorax" as reason specification).

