13. PATIENT DATA LISTINGS

1. Patient disposition

Listing 1.1. Study populations – Screened population

Listing 1.2. Inclusion/exclusion criteria – Screened population

Listing 1.3. Protocol deviations – Screened population

Listing 1.4. Study visits – Screened population

Listing 1.5. End of study information – Screened population

2. Demography and baseline characteristics

- Listing 2.1. Demographic data – ITT population
- Listing 2.2. Medical history and comorbidities – ITT population
- Listing 2.3. Lung tumor characteristics – ITT population
- Listing 2.4. Lung lesion details – ITT population
- Listing 2.5. Planning with the Epione® device – ITT population
- Listing 2.6. Procedure timing and duration – ITT population
- Listing 2.7. Follow-up visits – ITT population

3. Primary and secondary performance endpoint evaluations

- Listing 3.1. Primary endpoint: Needle(s) positioned accurately enough to allow the next step of the intervention – ITT Population
- Listing 3.2. Needle placement accuracy measured during intervention – ITT population
- Listing 3.3.1. Number and grading of needle adjustments – General information – ITT population
- Listing 3.3.2. Number and grading of needle adjustments – By patient – ITT population
- Listing 3.3.3. Number and grading of needle adjustments – By lesion – ITT population
- Listing 3.3.4. Number and grading of needle adjustments – By needle – ITT population
- Listing 3.4. Immediate post-intervention ablation success (ablation only) – ITT population
- Listing 3.5. Long-term performance of the intervention using the Local Tumor Progression rate (ablation only) – ITT population

4. Secondary safety endpoint evaluations

- Listing 4.1. Adverse Events (summary during intervention) – Safety population
- Listing 4.2. Adverse Events (details) – Safety population
- Listing 4.3. Adverse Device Effects (ADEs) – Safety population
- Listing 4.4. Serious Adverse Events (SAEs) – Safety population
- Listing 4.5. Serious Adverse Device Effects (SADEs) – Safety population
- Listing 4.6. Device dysfunction – Safety population

5. Other Listings

- Listing 5.1. Concomitant medications – ITT population
- Listing 5.2. Concomitant treatments related to AE/SAE – ITT population
- Listing 5.3. CT-scan details – ITT population

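### Per-patient ablation success takes the best lesion, so a patient with one complete and one incomplete or unclear ablation is tabulated as complete.

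*SAP*

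**What the plan says.** SAP section 9.2.3 introduces the endpoint: "This secondary criterion determines if the ablation is complete, incomplete or unclear". Section 3.5.2 defines the three categories for a targeted tumour, that is, at lesion level, and has them read on the final post-intervention scan. Each lesion therefore has one rating. For the tables, section 9.2.3 says that "summary statistics for qualitative parameters will be provided per lesion and per patient (the best result per patient"). No other section gives a different patient-level rule.

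Several lesions per patient are foreseen. The protocol synopsis (Study flowchart, Visit 2) sets a condition "In case of interventions on multiple lesions", and SAP section 7 summarises the "Number of lesions intended to be treated per lung per patient".

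Section 5.5.5 plans the endpoint by lesion and by patient, in the PP and ITT populations, at both interim analyses and the final analysis. It also says that the interim reports go into the sponsor's clinical data pool for regulatory purposes. The results appear in Tables 3.4.1 and 3.4.2, and section 13 adds "Listing 3.4. Immediate post-intervention ablation success (ablation only").

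**The concern.** With one rating per lesion, the best result per patient can only sensibly mean the best lesion. A patient with one complete and one incomplete or unclear ablation is then counted as complete. An extra lesion can improve a patient's category but never worsen it.

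A reader who sees a percentage of patients with complete ablation will probably take it to mean that nothing was left inadequately ablated in those patients. The rule does not measure that. A patient-level figure can also be quoted from the regulatory data pool without the lesion table beside it.

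The rule is also incomplete. The SAP does not rank incomplete against unclear, so the best result is undefined for a patient with one of each, and two programmers could produce different tables.

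**Working it through.** **Direction, from the text.** The plan gives no rate or calculation for this endpoint, so there is no figure to reproduce. Applying the rule to a patient with two ablated lesions gives:

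| Lesion results | Best result (SAP 9.2.3) | All lesions complete? |
|---|---|---|
| complete + complete | complete | yes |
| complete + incomplete | complete | no |
| complete + unclear | complete | no |
| incomplete + unclear | undefined (no order given) | no |
| incomplete + incomplete | incomplete | no |

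The two measures of complete ablation differ only for mixed results, and always in the favourable direction.

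**Comparison with other roll-ups in the SAP.** In section 9.2.2 the corrective distance per patient is the highest value, and the SAP explains: "The highest distance was considered as the worst distance". In section 9.1.1 a lesion is a technical failure "If insertion of one or several needle(s) from the skin is fully manual". The first is a patient-level rule and the second goes from needle to lesion. Both let the unfavourable component decide.

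**Size, under assumptions.** None of these inputs is in the documents: 20 ablation patients; *k* of them with two lesions and the rest with one; proportion *p* of lesions complete, with *q* = 1 − *p*; within-patient correlation *r*.

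For a two-lesion patient:

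- best result complete = 1 − (*q*² + *rpq*)
- all lesions complete = *p*² + *rpq*
- gap = 2*pq*(1 − *r*)

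Cohort rate = [(20 − *k*)*p* + *k* × two-lesion value] / 20.

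Example with *p* = 0.8, *r* = 0, *k* = 5. The two-lesion values are 1 − 0.04 = 0.96 and 0.64. The cohort rates are (15 × 0.8 + 5 × 0.96)/20 = 16.8/20 = 84% and (15 × 0.8 + 5 × 0.64)/20 = 15.2/20 = 76%, a difference of 1.6 patients.

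| *k* | *r* | *p* | Best result | All complete | Gap (patients of 20) |
|---|---|---|---|---|---|
| 5 | 0 | 0.7 | 75.25% | 64.75% | 2.1 |
| 5 | 0 | 0.8 | 84% | 76% | 1.6 |
| 5 | 0 | 0.9 | 92.25% | 87.75% | 0.9 |
| 5 | 0.5 | 0.7 | 72.6% | 67.4% | 1.05 |
| 5 | 0.5 | 0.8 | 82% | 78% | 0.8 |
| 5 | 0.5 | 0.9 | 91.1% | 88.9% | 0.45 |
| 2 | 0 | 0.8 | 81.6% | 78.4% | 0.64 |
| 10 | 0 | 0.8 | 88% | 72% | 3.2 |
| 0 | any | any | *p* | *p* | 0 |

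The gap also vanishes at *r* = 1, when the lesions of a patient always agree.

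**A separate, lesser point in section 3.5.2.** The second category reads: "INCOMPLETE ABLATION: GGO covers the targeted tumor but with a margin of <5 mm". Complete also requires coverage of the tumour. A tumour that is visibly not fully covered therefore fits neither category as worded.

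**The case against.** The strongest reply is that the SAP openly calls the row the best result per patient and never claims that it estimates the share of patients with all lesions complete. On that view it is an unhelpful summary rather than a biased one. It is true that the bias exists only relative to the all-complete reading. That reading is nevertheless the natural one for a patient-level rate of complete ablation. The appendix templates do not include Tables 3.4.1 and 3.4.2, so nothing shows that the row will carry a label that prevents it.

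The SAP also has no uniform worst-case convention. In section 3.2.1 a patient is withdrawn early only if all planned lesions fail technically, so one success keeps the patient in. That is correct, but the rule governs withdrawal and says nothing about how to summarise ablation success.

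A worst-result rule depends on lesion count too: an extra lesion can only lower the patient's result. This stands. It is acceptable if the patient-level question is whether any treated lesion was left inadequately ablated, because each lesion is a further chance of that.

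Replacing the rule could break comparability with an interim report already issued under it. The documents do not say whether one has been issued. Keeping the best result as a labelled second row preserves comparability.

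Finally, the impact is small and uncertain. The per-lesion summary and Listing 3.4 show every incomplete lesion. Section 9.2.3 specifies no confidence interval, test or threshold. Biopsy, drainage and fiducial placement are also eligible, so the number of ablations is unknown. All of this stands and limits the weight of the point.

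**Conclusion.** The concern holds. As written, section 9.2.3 gives a patient-level rate that can only overstate the share of patients whose ablated lesions were all complete, and it leaves the best result undefined for an incomplete-plus-unclear patient.

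With five two-lesion patients among 20 and 70% to 90% of lesions complete, the overstatement is 0.9 to 2.1 patients if lesions are independent and 0.45 to 1.05 patients at a correlation of 0.5. The cohort size, the number of multi-lesion patients, the lesion rate and the correlation are all assumptions. Only patients with several ablated lesions and mixed results are affected.

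The change should be made because the figure is planned for every analysis and for regulatory use. It does not touch the primary endpoint. The section 3.5.2 wording gap is a lesser matter, and this conclusion does not rest on it.

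**What to change.** In section 9.2.3, replace the best result per patient with the worst result per patient and state the order of the categories, for example incomplete, unclear, complete, from worst to best. A patient is then complete only if every ablated lesion is complete. If the best result is kept as well, for instance for continuity with an interim report, label it *at least one lesion completely ablated*.

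This costs one phrase and a category order, with no new data. The reported patient-level rate becomes less favourable wherever results are mixed. Section 4.2 already requires changes from the SAP to be discussed in the study report.

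Separately, clarify in section 3.5.2 that a tumour not fully covered by the ground glass opacity is tabulated as not complete (incomplete), subject to the categories in the assessment tool and CRF. This may cost more. Section 5.1 dates the first inclusion to 30 November 2022, so ratings may already have been made under the present wording. The CRF and tool categories would need checking, and some images might need re-reading.

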3.2. Study design

3.2.1. Study design and device

This is an interventional, prospective, non-comparative, non-randomized and single-arm study of a CE marked device, used outside of its intended use according to the Medical Devices Regulation MDR (EU) 2017/745.

The Epione® device is a Class IIa, non-invasive device and, as such, falls into Case #1 of the ANSM categorization (pre-market study category 1).

Eligible patients scheduled for an Epione® CT-guided intervention in the lung from the investigator's site will be proposed to participate. If they agree, they are enrolled. In case

the prescribed intervention is not maintained, the patient will be removed from the study without any impact on the inclusion window.

The inclusion period (recruitment) is estimated as 6 months for 25 patients (*i.e.* at least 25 CT-guided interventions in the lungs: at least 1 per patient). The inclusion rate will depend on the number of sites using the Epione® device routinely. Two study sites in France are expected to participate in this clinical investigation, Gustave Roussy (Villejuif) will be the coordinating center and a second site will be the Hôpital de La Timone (Marseille).

Considering the main criteria is feasibility, a technical failure of the whole intervention (for all the lesions planned in case of multiple lesions) leads to patient's premature end of study and study withdrawal. In this case, the only data available and analysable will be the technical success of lesion treatment (primary endpoint).

The study device is a user-controlled, stereotactic accessory intended to assist in the planning and manual advancement of the needle, as well as aiding the verification of needle position during CT-guided percutaneous ablation procedures.

The operating principle of the investigational device is detailed in section 6.2 of the protocol.

Five visits will be recorded in the CRF.

- **Visit 1** (within one month before treatment): the first visit is planned to screen the patient, present the study, and deliver the information notice and informed consent form.

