5.5.1. Summary statistics

Description of relevant study variables will be performed using n, number of missing data, mean, standard deviation, median, min and max for quantitative variables and

using number of missing data, frequency and percentage of non-missing for qualitative variables.

Analyses will be presented by patient, by lesion (when relevant) and/or by needle (trajectory). The statistical analysis will take into account data clustering (e.g. several procedures for a given patient) in case of inferential statistics.

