5.5.4. Handling of dropouts and missing data

Missing data will not be imputed, except dates (missing day) if needed in order to calculate durations.

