5.5.5. Interim analyses

Two interim analyses are planned to gather early evidence on the performance and safety of the device. The interim reports will be integrated in the clinical data pool of the Sponsor for regulatory purposes.

- The first interim analysis will be performed when the first 10 patients have been included in the study and have undergone the planned robotic intervention with data recorded and validated in the eCRF, enabling the primary and secondary endpoints related to the intervention to be analyzed. All possible tables and listings will be produced (summarized in table below).
- The second interim analysis will be performed when all 25 patients expected have been included in the clinical investigation, with the identical conditions detailed in the previous point. All possible tables and listings will be produced (summarized in table below).

Objective	Endpoint	Population	Method	1 st interim	2 nd interim	Final
Feasibility	Technical success of the intervention	PP and ITT	Lesion	X	X	X
Performance	Needle placement accuracy	PP and ITT	Needle	X	X	X
	Number and grading of needle adjustments	PP and ITT	Needle, Lesion, Patient	X	X	X
	Immediate post intervention ablation success	PP and ITT	Lesion, Patient	X	X	X
	Long-term performance of ablation using the LTP rate	PP and ITT	Lesion			X
Safety	Number of AE recorded	SP		X	X	X
	Number of SAE recorded	SP		X	X	X
	Number of SADE recorded	SP		X	X	X

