6. STUDY PATIENTS

6.1. Disposition of patients

The disposition of patients according to populations of analysis (Screened, ITT, PP, Safety) and visits (Visit 1 – Screening, Visit 2 – Intervention, Visit 3 – Follow up at 1 month, Visit 4 – Follow-up at 6 months and Visit 5 – Follow-up at 12 months, End of study) will be presented using frequency and percentages.

End of study information (normal end of follow-up (Visit 5 performed), AEs, screen failures, patient's will to withdraw from study, lost to follow-up, device deficiency or dysfunction, death and other) will be presented using frequency and percentages.

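### SAP 9.2.4 words a lesion-level LTP rate as a percentage of patients, and does not say that an LTP recorded at 6 months still counts at 12 months

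*SAP*

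**What the plan says.** **Unit.** SAP 9.2.4 states of LTP: "This will be presented by lesion only". A sentence later in the same section defines the statistic, with 95% confidence intervals: "Frequency and percentage of patients with any visible LTP on control imaging will be presented at approximately 6 months and 12 months". In the endpoint table of SAP 5.5.5, the row "Long-term performance of ablation using the LTP rate" has lesion as its only method. The row above it, immediate ablation success, has lesion and patient.

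**Time points and missing scans.**
- SAP 3.5.2 has LTP "evaluated from CT images at the 6 and 12 months" visits, with the 1-month scan as baseline.
- SAP 5.5.1 reports the number missing, together with "frequency and percentage of non-missing for qualitative variables".
- SAP 5.5.4 says: "Missing data will not be imputed". The only exception is incomplete dates.
- SAP 6.1 provides for follow-up that ends early. Its end-of-study reasons include "lost to follow-up, device deficiency or dysfunction, death and other".

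Neither the SAP nor the protocol synopsis says whether the 12-month figure is cumulative, or what happens to a lesion that has no 12-month image.

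**The concern.** There are two separate points.

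The first is wording. The sentence that carries the confidence interval counts patients, while its own section and the overview table count lesions. Several lesions per patient are foreseen, so the two units can give different rates.

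The second is a gap. Local progression, once seen, has happened. If each visit is summarised only over the lesions assessed at that visit, a lesion already recorded as progressed disappears from the 12-month rate when its 12-month scan is absent. The reported proportion with LTP could then fall between 6 and 12 months.

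LTP is the only long-term performance endpoint in a study meant to support extending the indication to the lungs. The 12-month figure is therefore likely to be quoted alone, without the missing count beside it.

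**Working it through.** The documents give no LTP rate, no number of ablated lesions and no dropout figure, so there is nothing to reproduce. All counts below are assumptions that show how the rules behave.

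**Unit.** Assume 35 ablated lesions in 25 patients, 4 of the lesions with LTP.
- By lesion: 4/35 = 11.4%.
- By patient, if the 4 lesions are in 4 patients: 4/25 = 16.0%.
- By patient, if they are in 2 patients: 2/25 = 8.0%.

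The unit can move the rate either way. With one ablated lesion per patient it makes no difference.

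**12-month rate over lesions scanned at 12 months.** Assume 20 ablated lesions, all assessed at 6 months. Four have LTP then, and one more has LTP by 12 months. True cumulative LTP is (4 + 1)/20 = 25.0%. Let *a* be the number of progressed lesions and *b* the number of LTP-free lesions without a 12-month scan. Take the *a* lesions from the four early progressions.

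Visit-wise rate = (5 − a)/(20 − a − b)

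- It is below 25.0% if b < 3a, equal at b = 3a, and above if b > 3a.
- It is below the 6-month 20.0% if 5 + b < 4a.

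| a | b | Visit-wise at 12 months | Against 25.0% |
|---|---|---|---|
| 0 | 0 | 5/20 = 25.0% | equal |
| 1 | 3 | 4/16 = 25.0% | equal |
| 0 | 4 | 5/16 = 31.3% | too high |
| 2 | 2 | 3/16 = 18.8% | too low, and below the 6-month rate |

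Clopper-Pearson 95% intervals, without a clustering allowance, are 5.7 to 43.7% for 4/20, 4.0 to 45.6% for 3/16 and 8.7 to 49.1% for 5/20.

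**Is carrying the event forward enough?** Keep every recorded LTP as an event but still drop unscanned LTP-free lesions: rate = 5/(20 − b). With a = 1 and b = 3 this is 5/17 = 29.4% against a true 25.0%. Events stay in while non-events leave, so the rate is biased upward.

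**Censoring instead.** Sixteen lesions are LTP-free at 6 months, and 16 − b of the 20 are followed on to 12 months.

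Cumulative LTP = 1 − (16/20) × (1 − 1/(16 − b))

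- b = 2: 1 − 0.8 × 13/14 = 25.7%
- b = 3: 1 − 0.8 × 12/13 = 26.2%

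These results depend on the one new LTP being scanned. Suppose that, with one progressed and three LTP-free lesions unscanned, the missing progressed lesion is the new one. Then 12 lesions remain under observation with no event, and the estimate is 1 − 0.8 × 12/12 = 20.0%. The visit-wise rate in that case is 4/16 = 25.0%.

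**Bounds for a = 1, b = 3, with the new LTP scanned.** The simple proportion over all ablated lesions is 5/20 = 25.0%, a lower bound. If all three unscanned LTP-free lesions had progressed it would be 8/20 = 40.0%.

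**The case against.** The unit slip is editorial, and the documents resolve it. The contrast between the lesion and patient rows in SAP 5.5.5 suggests that lesion alone was deliberate. This stands, and the first point is only a wording correction.

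On the second point, no section states a visit-wise rule. The phrase about any visible LTP can be read as cumulative, and counting an event already observed is arguably derivation and not imputation. Only a synopsis of the clinical investigation plan was supplied, so the full plan or the CRF may settle the matter. This also stands, as far as it goes: the text is underspecified and does not state an exclusion. But the same phrase is tied to control imaging at each time, and the general rules point to assessed lesions only. Two programmers could produce different tables from it.

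The consequence is limited. It needs a progressed lesion without a 12-month scan, and a list of end-of-study reasons is no evidence that this will occur. The missing count and Listing 3.5 would reveal the loss, both rates are shown, and the intervals are wide. All of this is right, and it is why no size is claimed.

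A reader might go further and infer that the plan will understate 12-month LTP. The documents do not support that. The error may be downward, nil or upward, depending on which lesions miss the scan, and no dropout figures are given.

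**Conclusion.** The unit wording is certainly inconsistent and should be corrected to lesions. The second point holds conditionally. If the general rules on non-missing percentages and no imputation are applied at each visit, a recorded LTP can leave the 12-month rate, which can then fall below the 6-month rate. The illustration is 20.0% falling to 18.8% when cumulative LTP is 25.0%, on assumed counts throughout.

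Direction and size in this trial cannot be established. A persistent LTP that is scanned again is unaffected, so there is no effect if all such lesions are rescanned. LTP is secondary and descriptive, and no test, threshold or primary result depends on it.

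Nor should a reader infer that a censored estimate is always closer to the truth. When the one new LTP is unscanned, it gives 20.0% against a true 25.0%. Its merit is that a recorded event is never lost and unscanned LTP-free lesions are handled by a stated assumption. The change is worth making before the final analysis, but it is not critical.

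**What to change.** In SAP 9.2.4:

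1. Replace the reference to patients with ablated lesions.
2. Report cumulative LTP by the 6-month window (4 to 8 months) and by the 12-month window (10 to 14 months). State that a recorded LTP remains an event at later time points.
3. Do not simply drop LTP-free lesions without a 12-month scan. Censor them at their last assessable scan, grouping scans by window.
4. Beside each rate, show the number of LTP-free lesions without a scan. Add the simple proportion over all ablated lesions, labelled as a lower bound.
5. Compute the 95% interval with the allowance for lesions clustered in patients that SAP 5.5.1 already promises, and name the method.

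The cost is a few sentences and slightly more programming, on data already collected. The 12-month figure may be less favourable. The estimate still assumes that unscanned LTP-free lesions progress like scanned ones, which is why their number has to stand next to it.
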